6.5 Vital signs, height, weight

The examination includes measurement of body temperature in the armpit, sitting blood pressure, pulse, respiratory rate. Changes of vital signs versus baseline values, regarded as AEs, should be appropriately reported in the source documentation and in CRF.

Weight and height of patients are measured with shoes off. Body mass index (BMI) is calculated according to the following formula: $BMI = \text{mass}/\text{height}^2$ (kg/m²), where mass is measured in kilograms, and height in meters.

6.6 Electrocardiography

12-lead electrocardiography (ECG) is performed in supine position. Investigator should review the ECG record, assess deviations (if any), sign and date the report.

6.7 Spirometry

Lung function assessment will be performed using regularly calibrated spirometric equipment according to the Federal clinical guidelines on spirometry by Russian Respiratory Community, 2013.¹³

To assess lung function and whether it meets study inclusion criteria, at Visit 1, Day 1 spirometry is performed pre- and post-bronchodilator, and registered spirometry parameters shall include:

- Pre-bronchodilator FEV1 \geq 70% of the predicted values,
- Post-bronchodilator FEV1 increase of \leq 12% or \leq 200 ml compared to the baseline,
- FEV1/FVC (Tiffeneau index) \geq 0.7

At visit on Day 8, spirometry is performed without bronchodilator, spirometry values will include FEV1.

The growth measure should be performed only during screening visit. For calculated values of lung function growth measured only at screening and weight measured during screening and Visit 3 (Day 8), should be used.

Tests should meet quality criteria for technical suitability and repeatability. To obtain reproducible results, at least three technically satisfying tests corresponding to acceptance criteria should be obtained; the best (maximum) result should be reported in the CRF.

Investigator should review the report of spirometry, assess test results, sign and date the report. Change of spirometry values versus baseline determined to be AEs should be appropriately reported in the source documentation and in CRF.

6.8 Six-point of daytime and nighttime cough assessment scale

Assessment of the severity and frequency of daytime and nighttime cough will be conducted with the "Six-point daytime and nighttime cough assessment scale" on visits to the center. Also, the patient will independently evaluate the severity and frequency of daytime cough (evening before retiring to bed) and nocturnal cough (in the morning after waking up) and enter the data in the patient diary.

"Six-point scale assessment of daytime and nighttime cough" is presented in Appendix 2. The patient will choose the most appropriate answer to the question and the corresponding points for the daytime and nighttime cough.

The investigator will record the results of the evaluation of severity and frequency of daytime and nighttime cough in the primary documentation and CRF.

6.9 Visual Analog Scale

The cough intensity will be assessed with Visual Analog Scale (Appendix 3). Visual analog scale is a 100 mm line where patient needs to mark cough intensity, where the extreme left point corresponds to no cough, and the extreme right point corresponds to severe cough of high intensity, significantly impairing daily activities. Investigator will measure the number of millimeters reported by patient with a ruler and report results in the source documentation and in CRF.

6.10 Patient Diary

During the period of study therapy, patients are on a daily basis to keep a diary in which to record the severity and frequency of daytime and nighttime cough, the investigational product intake, concomitant treatment, and adverse events occurred.

Also, patients will be advised to the measurement of body temperature twice a day: in the morning after waking and at night before retiring to bed.

6.11 Tests Performed at Local Laboratory

Local laboratory will be used for laboratory tests. Collection, preparation and storage of biological samples will meet requirements of the study site local laboratory.

At baseline, all local laboratories will provide the required certificates and laboratory reference values. Local laboratory is responsible for sending laboratory reports to the Investigator, and for reporting abnormal laboratory values to the Investigator. Investigator should review the laboratory report, all abnormal values should be assessed, signed and dated. Deviations of laboratory values from baseline, reported as AEs should be appropriately reported in the source documentation and in CRF.

Patient randomization is performed before laboratory test results are available. In case of significant abnormality which, at the Investigator's opinion, could interfere with patient's participation in the study or impact interpretation of efficacy or safety parameters, the patient should be withdrawn from the study.

6.11.1 Laboratory Parameters

Laboratory tests will be performed at predefined visits (D1 and D8) according to the Study Procedure Schedule (Table 1). Table 2 shows laboratory parameters which will be assessed in this clinical trial.

Table 2. Laboratory Blood Test Parameters

Blood Hematology	Blood Biochemistry		
Hemoglobin	Total Protein	Total cholesterol	Serum creatinine
Hematocrit	Albumin	Total bilirubin	
RBC		Conjugated bilirubin	GFR
WBC		ALT	
Neutrophils		AST	
Lymphocytes			
Monocytes			
Eosinophils			
Bazophils			
Platelets			
ESR			

Abbreviations: ESR – erythrocyte sedimentation rate, ALT – alanine transpherase, AST – aspartate transaminase, RBC - red blood cells, WBC - white blood cells, GFR - Glomerular filtration rate

Table 3 shows laboratory parameters of urine to be assessed in this clinical trial.

Table 3. Urine Laboratory Parameters

Clinical Urine Test	Special Tests
General properties: color, clarity, specific gravity, pH, protein, glucose, bilirubin, urobilinogen, ketone bodies, nitrites,	Pregnancy test (only for women of childbearing potential, including women at menopause of less than two years)

Clinical Urine Test	Special Tests
hemoglobin Sediment microscopy: epithelium, erythrocytes, leukocytes, casts, bacteria, salts	

6.11.2 Collection, Preparation, Storage and Delivery of Biological Samples

Collection, preparation, storage and delivery of biological samples will be performed according to normative regulations and local laboratory guidelines. The overall volume of blood collected from each patient during the study will be approximately 20 mL.

6.12 Assessment of Adverse Events (AE)

6.12.1 Definitions of AEs

Adverse Event (AE) – is any untoward medical occurrence in a clinical investigation subject administered a pharmaceutical product which does not necessarily have a causal relationship with this treatment. An adverse event (AE) can therefore be any unfavorable and unintended sign (including an abnormal laboratory finding), symptom, complaint or disorder. In this study AEs will be reported from the moment of signing Informed Consent Form (prior to administration of the first dose of the study drug) to Day 30 after the last visit of the patient or last procedure per protocol.

Adverse Drug Reaction (ADR) – any adverse event for which there is a reasonable possibility that the drug caused the adverse event. “Reasonable possibility” means there is evidence to suggest a causal relationship between the drug (at any dose) and the adverse event.

Serious Adverse Event (SAE) and/or Serious Adverse Drug Reaction (SADR) – Any adverse medical event which, irrespective of the dose of the study drug:

- results in death;
 - is life-threatening;
 - requires hospitalization (initial or prolonged);
 - results in significant, persistent or permanent impairment or disability; or
 - is a congenital anomaly or birth defect
- is an important medical event that may be not immediately life threatening or result in death or hospitalization but, based upon appropriate medical judgment, may jeopardize the patient and may require medical or surgical intervention to prevent one of the outcomes listed in the definition above.

Significant medical events that do not pose an immediate threat to life, do not result in death or hospitalization, but put patients at risk or require interventions aimed at the prevention of the above outcomes can also be included in SAE/SADR. Examples of such events may include bronchospasm of allergic genesis, convulsions, malignant neoplasms.

NOTE: Hospitalization for social reasons, visits to day patient facility, hospitalization or operation preplanned prior to patient enrollment into the study for treatment of underlying condition, are not to be considered SAEs.

Unexpected ADR – ADR of nature and severity not corresponding to the known information about the product (e.g. to the Investigator’s Brochure for unauthorized investigational product or to the prescribing information for authorized product). The group also includes ADRs specified in the investigator’s brochure as characteristic for the class of products

or expected as related to the pharmacological properties of the study product, but which had not been observed earlier.

Serious and Unexpected Suspected Adverse Reaction: Any suspected adverse reaction that is both serious and unexpected (SUSAR).

6.12.2 Pregnancy

Women of childbearing potential are not excluded from the study as long as adequate birth control methods are being utilized. Women of childbearing potential are defined as all women physiologically capable of becoming pregnant.

For the whole duration of the study, subjects must agree to use adequate contraception measures. Adequate birth control measures include:

- oral or transdermal contraceptives,
- condom or diaphragm (barrier method) with spermicide or
- intrauterine device.

Pregnancy is not a SAE, but refers to events that require an urgent reporting to the Sponsor. In case of pregnancy during the study, either occurring in a female patient or in a male patient's partner, the pregnancy status should immediately be reported to the Sponsor. Female patient will be withdrawn from the study and will be monitored throughout pregnancy and up to 30 days after its outcome. Health conditions of any newborn who was conceived during the study will also be followed up to 30 days after birth (including pregnancy of patient's partner). Relevant information will be recorded in source documents, CRF and Pregnancy Report Form. Pregnancy reports should be completed and e-mailed/faxed following the procedure described in Paragraph 6.12.7.

6.12.3 Reporting AEs and SAEs

At every visit, patients should report any AEs, responding to open, non-probing questions (e.g. How have you been doing since the last visit?). For each AE/SAE reported by a patient, the Investigator should collect and document in source documents and CRF all the needed information, including diagnosis and symptoms, date of onset and date of resolution, outcome, severity, criteria of seriousness, circumstances, that may denote possible relatedness to the study drug and concomitant therapy, underlying diseases or concomitant conditions, study procedures or other causes, actions related to the study drug, pharmaceutical treatment, medical interventions, results of laboratory and instrumental tests for AE, other circumstances, which may add to comprehensive description of the event

Within the period of self-administration of the study drug, patients will enter information about possible adverse events in a diary.

Increase in severity of the ongoing adverse event shall be considered a new AE. The date of further worsening in severity will be the start date of the new AE, and the previous day shall be the end date of the original AE.

The date of onset of SAE is the date of onset of the seriousness criterion. The preceding condition, if applicable, should be reported as a non-serious AE.

If an AE is serious, Investigator should also promptly submit a SAE report (specifying the seriousness criteria), within 24 hours from first knowledge to the IPHARMA Medical Monitor. New information about SAE which becomes known later, should be reported to the Sponsor in the same way and in the same time. Besides, the Sponsor should be provided with certified

copies of source documents for that SAE (hospital discharge summary, autopsy report, death certificate etc.). Data in source document and SAE form shall be duly anonymized.

AEs should be followed up and reported from the date of signing informed consent to the last visit or study related procedure (teleconference at follow-up). Any AE or SAE which is spontaneously reported by a patient within 30 days after the last study visit, will be reported and assessed in the same way as AEs occurring during the study. AEs should be reported until resolution or stabilization of patient's condition.

In line with ICH E2A provisions on Post-Study events, although such information is not routinely sought or collected by the Sponsor, serious adverse events that occurred after the patient had completed a clinical study (including any protocol-required post-treatment follow-up) will possibly be reported by the Investigator to the Sponsor. Such "post-study cases" should be regarded for expedited reporting purposes as though they were study reports. Therefore, a causality assessment and determination of expectedness are needed for a decision on whether or not expedited reporting is required.

Monitor is responsible for verifying compliance of CRF and SAE reports to the source documentation.

6.12.4 Assessment of AE Severity

For each AE, the Investigator will assess the severity grade. For that purpose the following severity grading scale is used:

1. Mild	Grade 1 - does not interfere with patient's usual function (awareness of symptoms or signs, but easily tolerated [acceptable]).
2. Moderate	Grade 2 - interferes to some extent with patient's usual function (enough discomfort to interfere with usual activity [disturbing]).
3. Severe	Grade 3 - interferes significantly with patient's usual function (incapacity to work or to do usual activities [unacceptable])

For each episode, the highest severity grade attained should be reported.

It should be noted that severe AEs not always comply with criteria of seriousness, while SAE is not always severe. The urgency of reporting of SAE does not depend on the severity of the event.

6.12.5 AE Relatedness to the Study Drug

For each AE the Investigator should assess its possible causal relationship to the study drug according to the Modified WHO scale/ICH E2B, shown in Table 4.

Table 4. Causal Relationship to the Study Drug

AE Category	Definition
1. None (Intercurrent Event)	An event that is not and cannot be related to the Investigational Product, e.g. patient is a passenger in a road traffic accident.
2. Unlikely (remote)	Relationship is not likely e.g. a clinical event including laboratory test abnormality with temporal relationship to drug administration which makes a causal relationship improbable and in which other drugs, chemicals or underlying disease provide more plausible explanations
3. Possible	Relationship may exist, but could have been produced by the patient's condition or treatment or other cause
4. Probable	Relationship is likely, the AE abates upon discontinuation of Investigational Product and cannot be due to the patient's condition
5. Highly Probable	Strong relationship, the event abates upon discontinuation of Investigational Product and, if applicable, re-appears upon repeat exposure

6.12.6 Assessment of Expectedness

Expectedness will be determined based on the contents of the Investigators' Brochure/SmPC as applicable for the suspected drug. Please also refer to Section 3.4.4 "Significant Potential Risks".

Expected	An adverse reaction, the nature or severity of which is consistent with the applicable product information (e.g. Investigators' Brochure)
Unexpected	An adverse reaction, the nature or severity of which is not consistent with information in the relevant source document (e.g. Investigators' Brochure)

6.12.7 Providing Reports about SAE/Pregnancy

All SAE irrespective of severity and relatedness to the study drug, as well as pregnancy cases should be reported to IPHARMA Medical Monitor and the Dompé Pharmacovigilance, by fax or e-mail, within 24 hours from the moment of first knowledge by the Investigator. Information about SAE should be sent in the form of SAE report. Information about pregnancy should be sent in the form of pregnancy report. In case of need Investigator may contact with Medical Monitor for consultation or explanations.

Reporting about SAE/pregnancy

IPHARMA LLC Medical department:

Medical Monitor: [name]

[contact]

[contact]

Mob.: [contact]

e-mail: [contact]

Dompé Pharmacovigilance:

[name], Safety Manager

Direct line: [name]; [contact]

[contact]

E-mail: [contact]

IPHARMA Medical Monitor will be then responsible for verifying consistence of information reported and data included in SAE/Pregnancy Report Form, obtaining and reporting any additional information received from the Investigators, and forwarding fully completed SAE/Pregnancy Report Forms to the Dompé Pharmacovigilance, by e-mail immediately and anyway within 24 hours of knowledge of event. **SAE reports with fatal outcome shall be transmitted to the Dompé Pharmacovigilance as soon as possible, and within a maximum of 12 hours from the time IPHARMA has knowledge of the death.**

Investigator should instruct each patient to report SAE or pregnancy during study and 30 days after the last visit to the study site or last study procedure. Investigator should provide in the SAE/pregnancy report form all information about the event. Each SAE report form should include at least the following information: patient details, event title, seriousness criterion, relatedness to the study drug, and outcome at the time of report.

For primary report the Investigator makes the following remark to the SAE report – “Primary report”. If additional information about SAE (for example, new information about patient condition or results of laboratory tests) occurs Investigator should fill in a new form of SAE report with “Additional report” mark. Original of SAE report form should be kept in Investigator File.

The Investigator (or an authorized staff member) will be responsible for reporting any SAEs/SUSARs to the Local Ethics Committee and local institutions in accordance with local regulations and requirements.

The Sponsor shall be responsible to prepare and approve Periodic safety reports and SUSAR report and to forward them the IPHARMA for submission. IPHARMA will be responsible Periodic safety reporting to the Regulatory Authorities in the Russian Territory and Investigators, and expedited reporting of SUSARs to the local Regulatory Authorities, in accordance with local regulations and requirements. The Sponsor will be responsible for regulatory reporting outside the Russian Territory, as applicable.

6.12.8 Overdose

Cases of overdose (accidental or intentional) which may or may not result in serious adverse reactions are to be reported by Investigator to IPHARMA and Sponsor Pharmacovigilance, following the same procedure for SAE, within 24 hours from the Investigator’s knowledge of its occurrence. This includes reports related to drug intake with suicidal intentions and consequent drug overdose.

An overdose of LEVOPRONT is defined as the administration of more than 30 ml (180 mg) on any given treatment day (with allowances of 120% compliance). An overdose of LIBEXIN is defined as the administration of more than 900 mg on any given treatment day, according prescribing information for LIBEXIN.

The Investigator shall provide in the SAE form information about symptoms, corrective treatment and outcome of overdose.

6.12.9 Emergency Procedures

Investigator is responsible for obtaining information about all emergency medical conditions of patients in the study. The Patient information leaflet and Informed consent form contains contact details of Investigator. Patients will be recommended to contact the Investigator in case of any emergencies during the study.

6.12.10 Assessment of AE with concomitant therapy

To assess relatedness of AE to concomitant therapy please refer to prescribing information for the drugs (State Register of Medicinal Drugs <http://grls.rosminzdrav.ru/GRLS.aspx>).

6.12.11 Clinically Significant Laboratory Abnormalities

Any clinically significant abnormalities of laboratory parameters or results of the instrumental methods of examination noted at screening shall be registered in the patient's medical history. After screening, new or worsened clinically significant abnormalities shall be reported as adverse events in source documents and CRF.

6.13 Early Withdrawal of Patients from the Study or Discontinuation of Study Treatment

The patient has the right to refuse to take part in the study at any stage without giving reasons.

The patient should be withdrawn from the clinical study if:

- Investigator considers it important from the medical point of view
- Patient withdraws his consent
- Patient does not comply with the study drug dosing regimen or study related procedures
- AE or SAE which may impact safety or well-being of patient
- Infection of lower respiratory tract
- Patient is included into the study with violation of inclusion/exclusion criteria

In the following cases immediate discontinuation of the study drug is required:

- Patient starts administration of another study drug
- Pregnancy in a study subject
- Significant protocol deviations that may impact patient's safety and integrity of the study data
- Use of prohibited drugs

If possible, the Investigator should discuss the need to withdraw the patient with the Medical Monitor or inform about patient withdrawal from the study within 48 hours. The reason for patient withdrawal should be specified in the source documents and in CRF. If a patient discontinues from the study for more than one reason, only the main reason should be specified. If a patient withdraws consent because of AE or SAE, the AE or SAE should be specified as the reason for patient withdrawal.

Besides, the Sponsor may terminate the study at any time. The Investigator has the right to terminate the study at any time for medical or regulatory reasons. Study may only be terminated after mutual consultations between the Investigator and the Sponsor.

If the study is terminated early, all patients should undergo procedures of early termination and all study materials should be returned to the Sponsor or his/her representative.

Follow up of AEs, SAEs and pregnancy ongoing at the time of study termination should be continued per protocol if not agreed otherwise between the Investigator and the Sponsor.

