7.5 Early Termination Visit

In case of early withdrawal from the study after Visit 1 (Randomization) and before Visit 3 (Day 8) the patient should be invited to the study site for early termination visit (ETV). Investigator should make all reasonable efforts to perform all the required assessments at the ETV. Early termination visit should occur not later than on Day 3 after the last dose of the study drug.

ETV should include all procedures of Visit 3, (Day 8). If ETV cannot be performed in full volume, the Investigator should agree his/her actions with the Medical Monitor.

At ETV the patient should return to the site all used and unused packages of the study drug. The patient will be given recommendations for further treatment within standard ARVI treatment options.

If possible, the Investigator should discuss patient withdrawal with Medical Monitor in advance. Otherwise, the Investigator should contact the Medical Monitor within 24 hours after the early termination visit.

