#### **5.2 INTENT-TO-TREAT POPULATION**

The population of patients is based on the initial treatment assignment and not on the treatment eventually received (ITT).

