## 6. HANDLING OF MISSING VALUES

### 6.1 EFFICACY PARAMETERS

Replacement of missing data is not planned for efficacy parameters.

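### Early withdrawal ends observation before Day 8, and the SAP leaves undefined how these patients enter the supportive ITT analysis of the primary endpoint (Table 9.9)

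*Protocol*

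**What the plan says.** Protocol 6.13 has two lists. The first gives reasons for leaving the study. It includes "Patient does not comply with the study drug dosing regimen or study related procedures", "AE or SAE which may impact safety or well-being of patient" and "Infection of lower respiratory tract". The second opens with "In the following cases immediate discontinuation of the study drug is required" and concerns study drug only; it does not say whether Visit 3 still takes place. Protocol 4.4 adds withdrawal for significant laboratory abnormalities found after randomisation. Nowhere is a withdrawn patient kept under observation to Day 8.

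Protocol 7.5 provides an early termination visit with all Visit 3 procedures, which include the six-point cough scale. On timing: "Early termination visit should occur not later than on Day 3 after the last dose of the study drug". The schedule (Protocol Table 1, SAP Table 2.1) puts this visit in the same column as Day 8, whose window is ±1 day.

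SAP 5.2 defines the ITT set as "based on the initial treatment assignment and not on the treatment eventually received". SAP 6.1 says: "Replacement of missing data is not planned for efficacy parameters". Protocol 9.9 states that missing data will not be substituted, then names LOCF for the efficacy endpoints, then lists two sensitivity analyses: missing as failure, and no substitution. SAP section 2 makes the SAP the leading source for the analyses.

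The primary population is PP (Protocol 9.4.1, SAP 5.1). SAP Table 9.9 repeats the primary analysis in the ITT set, with rows for ongoing and resolved cough and none for missing.

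**The concern.** An ITT analysis by assigned arm needs an outcome for every randomised patient, including those who stopped treatment. The reasons for withdrawal here (poor adherence, adverse events, a worsening infection) are related to treatment and to outcome. If these patients have no Day 8 score and nothing is put in its place, Table 9.9 can only count those who were observed. It would then resemble PP, which excludes non-completers by definition, and could not show a difference between arms in how often patients fail by leaving.

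Using the early termination score as if it were Day 8 raises another problem. Acute cough tends to resolve by itself, so a score from Day 4 or 5 is not comparable with one from Day 8.

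Unequal withdrawal is possible: the trial is open-label and compares a syrup with a tablet. The Table 9.9 result is the SAP's only listed ITT repeat of the primary analysis.

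**Working it through.** **1. The plan's own figure.** Inputs from Protocol 9.2: 70% response in both arms, margin 20 points, one-sided alpha 0.025 (z = 1.96), power 80% (z = 0.84), early discontinuation up to 10%.

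n = (1.96 + 0.84)² × (0.70×0.30 + 0.70×0.30) / 0.20² = 7.84 × 0.42 / 0.04 = 82.3 per arm. Then 82.3 / 0.9 = 91.5, rounded up to 92 per arm, 184 in total. This reproduces. The ceiling of 10% is about 9 of 92 per arm, or about 18 of 184.

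**2. Timing of the early termination visit.** Latest day allowed = day of last dose + 3. The Day 8 window is Day 7 to Day 9.

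- Last dose on Day 1, 2 or 3: visit by Day 4, 5 or 6, always before the window.
- Last dose on Day 4 or later: visit can be on Day 7 or later, inside the window, but nothing requires that.

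**3. Effect of the missing-data rule.** The SAP's method (7.2.3) is Newcombe's hybrid score. With Levopront as 1 and Libexin as 2:

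L = (p1 − p2) − √[(p1 − l1)² + (u2 − p2)²],

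where l1 is the Wilson lower limit for Levopront and u2 the Wilson upper limit for Libexin, both at z = 1.96. Non-inferiority needs L above -20 points.

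Assumptions: 92 randomised per arm, about 70% response among patients with a Day 8 score (rounded to whole patients), withdrawn patients without a usable Day 8 score, and about 18 withdrawals in total. The documents do not give the split between arms; two splits are shown.

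| Withdrawn (Levopront vs Libexin) | Rule | Responders | p1, l1 | p2, u2 | L |
|---|---|---|---|---|---|
| 9 vs 9 | observed cases | 58/83 vs 58/83 | 69.9, 59.3 | 69.9, 78.7 | -13.8 |
| 9 vs 9 | missing as failure | 58/92 vs 58/92 | 63.0, 52.8 | 63.0, 72.2 | -13.7 |
| 14 vs 4 | observed cases | 55/78 vs 62/88 | 70.5, 59.6 | 70.5, 79.0 | -13.8 |
| 14 vs 4 | missing as failure | 55/92 vs 62/92 | 59.8, 49.6 | 67.4, 76.1 | -21.0 |

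With balanced withdrawal the rule makes no practical difference. With 14 versus 4 the observed-case table shows a difference of about 0 and passes, while missing as failure gives 59.8 − 67.4 = -7.6 points and fails.

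**4. What missing as failure cannot show.** Take 9 versus 9 and suppose (an assumption) that the 9 on Levopront all truly failed while 6 of the 9 on Libexin responded. The true result is 58/92 versus 64/92, a difference of -6.5 points with L = -19.8, just inside the margin. Missing as failure would report 58/92 versus 58/92, a difference of 0. Only an observed Day 8 score reveals such a pattern.

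**The case against.** A reader might infer that withdrawn patients have no Day 8 score, that Table 9.9 is the only check on the PP result, and that it cannot be a true ITT analysis. The documents do not support any of these in full.

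- The early termination visit collects the cough score, and for later stoppers it can fall inside Day 8 ±1.
- Protocol 9.9 names LOCF and a missing-as-failure analysis. Either can keep all randomised patients in the denominator, although neither gives a score observed at Day 8.
- One cannot say what Table 9.9 would show, because its shell fixes neither the denominator nor the status of early termination scores.

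These objections stand, and they limit the point to what is undefined or in conflict. They do not remove it. No rule makes the early termination score a Day 8 score, Protocol 9.9 contradicts itself, and the SAP drops both of the methods that would keep everyone in.

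It can also be said that following patients after they start another cough medicine is one choice of estimand among several, and that such scores can pull the arms together and favour non-inferiority. That is correct. It is a reason to show the missing-as-failure result alongside.

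Finally, PP is primary and the harm depends on unbalanced withdrawal, for which the documents give no evidence. Both are true, and they limit the weight of the point.

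**Conclusion.** The point holds for the supportive analysis. Withdrawal from the study is tied to stopping treatment, no Day 8 assessment follows, the status of an early termination score is undefined, and Protocol 9.9 and SAP 6.1 disagree on missing values. Read with SAP 6.1, Table 9.9 may be close to a complete-case analysis.

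The size depends on the balance of withdrawals: no practical effect at 9 versus 9, and a reversed conclusion (-13.8 against -21.0) at an assumed 14 versus 4. The total of about 18 is the protocol's planning ceiling and not an observed rate. The primary PP analysis is unaffected. The change should be made because it is cheap and because the ITT result is there to expose bias in PP.

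**What to change.** Leave the stopping criteria as they are.

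1. **Protocol 6.13 and 7.5, Part 2:** record the Day 8 (±1) six-point score, by visit or telephone, for every randomised patient who has not withdrawn consent, whichever list in 6.13 applies. Note any other cough medicine taken. Use this score in Table 9.9.
2. **Both documents:** state that an early termination score outside Day 8 ±1 is not a Day 8 score.
3. **SAP 6.1 and Table 9.9:** reconcile with Protocol 9.9 by carrying over the missing-as-failure analysis on all randomised patients. This covers Part 1, where no further scores can be collected, and any gaps left in Part 2. Add a row for missing scores.

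Cost: a short amendment for Part 2, a few lines in the SAP, and one contact per early stopper. The patient chooses the score (Protocol 6.8) and a Day 10 telephone call already exists (7.3.1), so the added burden is small. The ceiling is about 18 early stoppers in the whole trial; Part 2 is only a portion of it, and the documents do not give the size of Part 1.

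Downside: some scores will be taken after other treatment has started, which can dilute differences towards non-inferiority. Report the missing-as-failure result next to them.
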